3.2. Inclusion Criteria

1. Male or female subjects between the ages of 13-75. The goal for the extended arm is that 50% of subjects will be 65 years of age or younger, and 50% will be older than 65¹⁴.
2. Subject must have distance BCVA measured with ETDRS of between 20:60 and 20:400 in the better eye.
3. Subjects have been diagnosed with a condition that presents as one or all of the following: Central scotomata, geographic atrophy, or scattered scotomata. These are typically symptoms attributed to conditions such as: Diabetic Retinopathy, Stargardt's Disease, Age Related Macular Degeneration, Leber's Disease, Retinopathy of Prematurity, Cone Rod Dystrophy, or Ocular Albinism¹⁵.
4. Subject must have an estimated functional field of view of at least 20 degrees (bilateral or monocular).¹⁶
5. If the subject is employed, they must be prepared to use eSight Eyewear in their workplace environment, have informed their employer of their involvement in the study, and received permission from their employer to bring eSight Eyewear into the workplace. If the subject is self-employed, they must be prepared to use eSight Eyewear in their

¹³ "Sample size estimation and power analysis for clinical research studies", Suresh & Chandrashekar, J Hum Reprod Sci. 2012 Jan-Apr; 5(1): 7-13. "G*Power 3: a flexible statistical power analysis program for the social, behavioral, and biomedical sciences", Erdfelder, Faul, & Buchner, Behav Res Methods. 2007 May;39(2):175-91.

¹⁴ The intention of this stratification of the cohort is to understand age effects related to the eSight Eyewear device. This stratification does not impact the statistical analysis in Section 3.1

¹⁵ These have been demonstrated by current eSight users to be conditions for which eSight Eyewear can provide significant benefit. For other conditions, especially those which present as peripheral degeneration encroaching inwardly ultimately towards the central vision, eSight Eyewear's effectiveness has not yet been convincingly demonstrated (e.g.: early stage Retinitis Pigmentosa, early stage Glaucoma).

¹⁶ Acuity and field criteria, while firm requirements here, are inflection points in the real world population. Evidence indicates that eSight users outside of the 20/60 – 20/400 BCVA and 20° field can still have success with the eSight device, but results are less consistent.

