²² The MoCA scoring tool does not provide regarding pass/fail criterion. Ultimately, a subject’s performance in the test is meant to provide clues to the researcher about cognitive deficiencies.

²³ Ware, Sherbourne. “The MOS 36-item short-form health survey (SF-36). I. Conceptual framework and item selection”. Med Care. 1992 Jun;30(6):473-83.

²⁴ Ware JE, Gandek B. Overview of the SF-36 Health Survey and the International Quality of Life Assessment (IQOLA) Project. J Clin Epidemiol. nov 1998;51(11):903-12.

²⁵ References: The forms provided with this study are a subset of LV rehabilitation practice guidelines from the following sources:

- a) Ontario Practice Template - Low Vision Assessment.
- b) New York Lighthouse for the Blind LV Intake Exam ([name]) <http://www.lighthouse.org/professionals/practice-management/structured-low-vision-exam>.
- c) VisionAware: <http://www.visionaware.org/info/your-eye-condition/eye-health/low-vision/low-vision-examination/1235>

determined in step 1.04 is substantially different from the subject's habitual glasses, this portion of the protocol may be conducted with a trial lens frame.

Step 3.04 Medical and Ophthalmic History: The clinician and/or site administrator will record the following information on the CRF:

- OD and OS disease type(s), and approximate number of years, if possible.²⁶
- Free-form field: other eye-health related history (e.g.: laser photocoagulation, Lucentis, etc.), considered by the examiner to be relevant.
- subject's verbal description of visual scotoma if present

Step 3.05 Refractive Prescription: The clinician will perform a refraction to determine the prescription lenses required by the subject for best distance and near vision. Note: No prism element may be included in the refraction prescription.

Step 3.06 Acuity Test: Choose ONE OF ETDRS or Snellen

ETDRS²⁷: Using the subject's habitual corrective lenses (if applicable). For each eye independently, and then binocularly, determine the ETDRS acuity.

- Determine the last row where the subject can correctly identify all 5 letters on that row.
- Determine the log score for that row (these scores are shown in the margin of the ETDRS test, e.g. the 20/25 line has a log score of 0.1)
- subtract 0.02 log units for every letter that is correctly identified beyond the last row where all of the letters are correctly identified.

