For example: if the subject reads all of the letters correctly on the 20/32 row and then 3 letters correctly on the 20/25 row, the Log Score would be calculated as follows:

$$\begin{aligned} \text{ETDRS Acuity Log Score} &= 20/32 \text{ Row} = 0.20, \text{ plus } 3 \text{ letters on } 20/25 \text{ row} \\ &= 0.20 - (3 \times 0.02) \\ &= 0.14 \end{aligned}$$

Snellen: Using the Subject's habitual corrective lenses (if applicable). For each eye independently, and then binocularly, determine the Snellen acuity²⁸.

Step 3.07 Mars Contrast Sensitivity Test: Test Contrast Sensitivity using the Mars chart. Mars test score sheet to be provided²⁹.

²⁶ On the CRF this will be a date range, because subjects will not recall with accuracy. E.g.: <6mos, 6-12mos, 1-2yrs, 2-5yrs, 5-10yrs, >10yrs.

²⁷ <https://www.good-lite.com/Details.cfm?ProdID=639>

²⁸ In some cases (e.g. dense scotoma) the test Subject may have difficulty reading ALL 5 letters on any line of the ETDRS chart, which limits the precise ETDRS scoring algorithm above. Adding Snellen allows greater flexibility in participant inclusion and data analysis.

²⁹ © 2003-2004 The Mars Perceptrix Corporation. <https://www.good-lite.com/Details.cfm?ProdID=549&category=26&Secondary=71>

Step 3.08 eSight Demonstration: eSight Eyewear will be demonstrated using a clinician's version of the device³⁰. The subject will be provided basic instruction on its use (zoom in/out, contrast adjust). The researcher will observe the Subject's performance in tests of, acuity (ETDRS) contrast performance, facial recognition, and reading (MNRead). These above tests are observational only, and are not recorded to provide a baseline performance measure with the eSight Device.

Step 3.09 Advancement Decision: At this point in the protocol the Subject and the Eyecare Physician will come to an agreement about whether to continue with the extended portion of the protocol evaluating eSight Eyewear. The decision will be based on a minimum 4-line ETDRS improvement using the device, the subject's performance of the various tasks above, their impressions of the eSight Eyewear demonstration, and the continued compliance with inclusion/exclusion criteria as defined in Sections 3.2 and 3.3 respectively. There is a subjective and personal aspect to this decision, not unlike a patient's decision about whether or not to purchase the device.

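### The Step 3.06 ETDRS rule gives no score without a complete row and leaves 'last row' ambiguous, and its Snellen fallback lets the acuity change mix scales

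*Combined protocol and SAP*

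**What the plan says.** Section 4.1, Step 3.06, scores ETDRS acuity in two moves. The examiner is first told: "Determine the last row where the subject can correctly identify all 5 letters on that row". From that row's log score the examiner must then "subtract 0.02 log units for every letter that is correctly identified beyond the last row where all of the letters are correctly identified". The one worked example is the case "if the subject reads all of the letters correctly on the 20/32 row and then 3 letters correctly on the 20/25 row", which gives 0.14. It is silent on larger rows and on what to do if no row is complete.

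The step is headed "Step 3.06 Acuity Test: Choose ONE OF ETDRS or Snellen". Footnote 28, giving dense scotoma as its example, warns that "the test Subject may have difficulty reading ALL 5 letters on any line of the ETDRS chart, which limits the precise ETDRS scoring algorithm above". Its stated remedy is the second chart: "Adding Snellen allows greater flexibility in participant inclusion and data analysis". Steps 4.02 and 9.03 repeat the choice of chart. No conversion between charts is given, and nothing requires a subject to stay on one chart.

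Section 3.2, criterion 3, recruits subjects whose condition presents as "Central scotomata, geographic atrophy, or scattered scotomata". Criterion 2 sets the acuity range (20:60 to 20:400) by ETDRS, and Step 3.09 includes a gain of at least 4 ETDRS lines. Section 10 lists acuity in the minimum data to be reported, without the device at the start against with it at the end.

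**The concern.** A scotoma can hide single letters on rows that are otherwise well above threshold. A rule anchored on a perfect row is therefore fragile in the very population being recruited. Three things are at stake.

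- **No ETDRS score.** With no complete row the rule yields nothing, however many letters are read. Criterion 2 and the 4-line criterion then have no ETDRS value to work from under the written rule.
- **Two scores from one set of responses.** 'Last row' has two natural readings. Sites could apply either, which adds to the inter-site differences that Section 10 wants to minimise.
- **Mixed scales.** A subject may have no complete row without the device and several with it. Such a subject could be tested on Snellen at Step 3.06 and on ETDRS at Step 9.03, and the Section 10 change would then subtract one scale from another.

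**Working it through.** **The plan's own example.** 0.20 - 3 x 0.02 = 0.14, as stated. By letter count, with an assumed top row of 1.0, 0.1 steps and all larger rows complete, there are 9 rows from 1.0 to 0.2. That is 9 x 5 + 3 = 48 letters, and 1.1 - 0.02 x 48 = 0.14. The two agree.

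**Three scorings compared** (same assumed chart):
- A: 'last row' is the smallest complete row.
- B: 'last row' ends the unbroken run of complete rows from the top.
- Letter count: (top row + 0.1) - 0.02 x all letters correct.

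| Letters read, from row 1.0 down | A | B | Letter count |
|---|---|---|---|
| 5, 4, 4, 5, 3 | 0.70 - 0.06 = 0.64 | 1.00 - 0.02 x 16 = 0.68 | 1.1 - 0.02 x 21 = 0.68 |
| 4, 4, 5, 2 | 0.80 - 0.04 = 0.76 | none | 1.1 - 0.02 x 15 = 0.80 |
| 4, 4, 3, 2 | none | none | 1.1 - 0.02 x 13 = 0.84 |

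A is better (lower) than the letter count by 0.02 for each letter missed above the anchor row. B equals the letter count whenever it gives a score, because each complete row is worth 5 x 0.02 = 0.1.

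**How often, and how much.** The documents give no miss rates, test distance or top row, so every input here is assumed: logistic threshold 0.8 without and 0.4 with the device, spread 0.06, rows down to -0.3, and a constant share of legible letters lost.

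Share with no ETDRS score:

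| Top row, reading | 10% lost: without / with device | 20% lost: without / with device |
|---|---|---|
| 1.0, A | 37% / 1% | 62% / 13% |
| 1.0, B | 51% / 41% | 73% / 67% |
| 1.3, A (without device only) | 3% | 19% |
| 1.6, A | about 0% | 6% / 1% |

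The eligibility limit of 20:400 is log10(400/20) = 1.30, so a 1.0 top row cannot cover the eligible range. The 1.3 row of the table is the better guide if the chart is matched to the population.

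Gain (without minus with device) under A minus gain by letter count, in the same scored subjects:
- Equal losses in both conditions, top row 1.0: 0.380 - 0.347 = +0.033 at 10%; 0.355 - 0.303 = +0.052 at 20%. With a 1.6 top row, about +0.04 and +0.07.
- Losses only without the device: -0.003 (10%) and -0.007 (20%) with a 1.0 top row; about -0.03 and -0.04 with a 1.3 top row.
- If the number of uncounted misses is equal in both conditions, the difference is zero. Under B it is zero throughout among scored subjects.

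**The case against.** Four points on the other side carry weight.

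1. **Snellen is offered for exactly this problem.** A reader might infer that scotoma patients go without any acuity score. That is not so: they lack an ETDRS score. What Snellen does not repair is criterion 2 and Step 3.09, which are in ETDRS terms, and the freedom to change chart between visits.
2. **A reader might infer that the rule overstates the device's benefit.** The documents do not support a direction. It needs reading A and similar miss rates in both conditions. Losses confined to the without-device test reverse the sign, and reading B removes the effect among scored subjects.
3. **Letter count is not the truth either.** The simulated threshold shift is 0.40. At 10% equal loss, A gives 0.380 and the letter count 0.347, so A is nearer. The case for letter counting is that it is always defined and read one way, not that it recovers the threshold better.
4. **The size is modest.** A difference of 0.03 to 0.05 log is 1.5 to 2.5 letters, against 4 x 5 = 20 letters for the 4-line criterion. That decision is also partly subjective, and it rests on Step 3.08 tests that are not recorded, so no effect on it has been shown.

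A reader might also take acuity to be the primary outcome. Section 10 lists it with contrast and reading speed and names none as primary.

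**Conclusion.** The point stands as a fault of definition. The rule is undefined when no row is complete, which the protocol itself concedes; it has two readings when letters are missed on larger rows; and the Snellen alternative comes without a same-chart or conversion rule. The reported acuity change can therefore mix scales.

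This much follows from the text alone. The sizes do not: the shares without a score, and the differences in gain of either sign, rest on assumed thresholds, spread, miss rates and top row. They show that the fault can matter, not how large it will be here. The sample size is unaffected, since Section 3.1 rests on a standardized effect of 0.40 to 0.45 and not on an acuity SD.

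**What to change.** Amend Step 3.06 and the CRF formula, and apply the change to every recorded ETDRS reading (Steps 3.06, 4.02 and 9.03):

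- Score = (log score of the top row presented + 0.1) - 0.02 x total letters correct, with the same formula, starting row and stopping rule with and without the device.
- State a test distance whose top row covers the 20:400 limit (1.3 log). With a 1.0 top row the formula cannot score worse than 1.1, so the worst eligible eyes would be floored.
- Use the same chart for a subject at all visits. Snellen is then no longer needed merely because no row is complete. Analyse any Snellen-only subjects separately.

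The cost is a paragraph and a spreadsheet formula, with the examiner marking each letter. Some scores will be a few letters worse than under the present rule.

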This study seeks to generate further evidence-based conclusions about the efficacy of eSight Eyewear for various ADLs in the low vision population. Specifically, the study seeks to understand how eSight Eyewear can be used to improve employee productivity and satisfaction in vocational, educational, and home settings.

An initial assessment was performed by the CNIB where 33 individuals of various age, vision and eye pathologies showed improved visual function for both distance and near vision using traditional visual assessment tests (distance acuity and contrast performance) using various image processing algorithms including variable magnification, adjustable contrast, and colour remapping techniques. The CNIB test did not include assessment of the Activities of Daily Living (ADLs) or seek to measure improved functional vision. To date there are ~400 “early-adopter” individuals with low-vision that wear the glasses in their day-to-day lives. Most users self-report high satisfaction with the device however, the technology has not been subject to rigorous scientific study to determine which users would most benefit from using this technology and how the glasses improve their functional visual performance and quality of life. Considering the high cost of this technology (\$15,000) this Clinical Study will guide patients and physicians on the expected benefits and indications for the large population affected with untreatable vision disorders.

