3.1. Sample Size

Subjects will undergo an initial screen and device demonstration (screening arm) to determine their suitability for an extended trial of the device (extended arm). The target number of subjects for the extended arm is 60 subjects.

Power analysis indicates that in a single tailed test with an alpha level of .05 and a power of .95, the relationship between anticipated effect size and the required sample size is shown in the chart at left. As indicated if we assume an effect size in the range 0.40 – 0.45¹², an appropriate n=60 (ten Study subjects per site).

¹¹ The term “functional visual performance” describes the wearer’s ability to perform various Activities of Daily Living (ADL) with better efficacy and speed than using habitual assistive technology devices. In some cases, because of the hands-free, variable distance, and portable attributes of eSight Eyewear, it is hypothesized that certain ADLs may be possible which were previously impossible or very difficult for certain subjects.

¹² This higher than typical anticipated effect size is an appropriate assumption for this Study design, because of prescriptive inclusion criterion (i.e.: not random population).

About $\frac{1}{3}$ to $\frac{1}{2}$ of subjects who fall into the acuity and visual field inclusion criterion described in Section 3.2 below, demonstrate acute objective improvement and an immediate aptitude with the device. Therefore, we anticipate a total of 150-200 to be enrolled in screening arm of the study, from which 60 will be selected to participate in the extended arm, a three month take-home trial of the device. We expect attrition to be low due to the rigorous screening process for participation.¹³

In addition to a clinician's unit, which incorporates trial lens frames and other unique features for fitting and demonstration, each Site will receive devices for Subjects as they are required. The Site and eSight can, at any time, agree to deploy additional devices to accelerate the collection of data.

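### Extended-arm entry depends partly on a 4-line gain on the device, so the reported acuity gain describes subjects who passed the demonstration. Section 10 does not say so, and no device response need be kept for those who do not advance.

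*Combined protocol and SAP*

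**What the plan says.** **Selection.** Section 3.1 states that a third to a half of subjects meeting the acuity and field criteria "demonstrate acute objective improvement and an immediate aptitude with the device", and so "we anticipate a total of 150-200 to be enrolled in screening arm of the study, from which 60 will be selected". Footnote 12 notes that the population is not random, as its reason for a larger assumed effect size. At Step 3.09 (Section 4.1), "The decision will be based on a minimum 4-line ETDRS improvement using the device", together with task performance, the subject's impressions and continued eligibility. The step adds: "There is a subjective and personal aspect to this decision".

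**Recording.** At Step 3.08 the subject tries the device on acuity, contrast, faces and reading. The plan says: "These above tests are observational only, and are not recorded to provide a baseline performance measure with the eSight Device". On-device acuity is first scheduled as a study test at Step 4.02, after selection. A subject who does not proceed has that fact and the reason entered on the CRF.

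**Analysis.** Section 10 sets as minimum reporting acuity, contrast and reading speed, without the device at the start and with it at the end. It names no analysis population and no analysis of the screening arm. Its limitations text covers site differences and short follow-up.

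**Aims.** Section 1 says that "this Clinical Study will guide patients and physicians on the expected benefits and indications for the large population affected with untreatable vision disorders". The last objective in Section 2 includes characterising the subjects whom the device helps little or not at all.

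**The concern.** The quantity used to admit subjects, the acuity gain on the device, is the same kind of quantity that Section 10 reports as a result. Choosing people with a large gain raises the average gain in those chosen. Given the aim in Section 1, a reader could take the figure from the 60 as what an eligible patient can expect, when it is what a patient who has already done well at a demonstration can expect.

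The objective about poor responders is also at stake. Those with little gain at the demonstration are largely the people screened out at Step 3.09, and the text does not require their response to the device to be kept. The tests are carried out anyway, but an unrecorded reading may not be recoverable later.

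**Working it through.** **1. The plan's own sample size.** Inputs from Section 3.1: one-sided alpha 0.05, power 0.95, effect size 0.40-0.45. For a paired comparison, n = ((1.645 + 1.645)/d)².

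- d = 0.40: (3.290/0.40)² = 67.6, so 68.
- d = 0.425: 59.9, so 60.
- d = 0.45: 53.5, so 54.

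The stated 60 lies inside this range. By the noncentral t it matches d of about 0.43.

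**2. How many do not enter.** From Section 3.1:

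- 150 - 60 = 90, and 90/150 = 60%.
- 200 - 60 = 140, and 140/200 = 70%.
- The stated third to a half gives 1 - 1/2 = 50% to 1 - 1/3 = 67%.

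Some of these may leave at Step 2.04 or Step 3.02, before any demonstration.

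**3. What is required for a subject who stops at Step 3.09**

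| Item | Required? | Where |
|---|---|---|
| Diagnosis and history | yes | Step 3.04 |
| Acuity and contrast without the device | yes | Steps 3.06, 3.07 |
| Decision and reason | yes | Step 3.09 |
| Acuity or contrast with the device | not required | Step 3.08 |

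**4. Illustrative size of the excess.** The scoring example at Step 3.06 makes one line 0.1 log unit, so four lines are 0.40. The documents give no mean or SD for the gain and no measurement error, so the following are assumptions:

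- the 4-line minimum is the only gate;
- a share p = 30-50% pass, spanning 60/200 to the stated one half;
- the true gain is normal with SD s = 0.10-0.30;
- each reading has error SD e = 0.05-0.10;
- true gain is the same at the demonstration and at month 3;
- the unaided reading at Step 3.06 serves both for the gate and as the reported baseline.

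Demonstration gain = true gain + baseline error - demonstration error, with SD T = √(s² + 2e²). Final gain = true gain + baseline error - final error. With k(p) the mean of the upper fraction p of a standard normal, which is its density at the cut-off divided by p:

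excess = k(p) × (s² + e²)/T

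- **Low end:** p = 0.50, k = 0.798, s = 0.10, e = 0.05, T = √0.015 = 0.1225. Excess = 0.798 × 0.0125/0.1225 = 0.081.
- **Middle:** p = 0.40, k = 0.966, s = 0.20, e = 0.08, T = √0.0528 = 0.2298. Excess = 0.966 × 0.0464/0.2298 = 0.195.
- **High end:** p = 0.30, k = 1.159, s = 0.30, e = 0.10, T = √0.11 = 0.3317. Excess = 1.159 × 0.10/0.3317 = 0.349.

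The part due to regression to the mean in the baseline, k × e²/T, is 0.006-0.067 over the same ranges. The rest is selection on true gain.

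If true gain at month 3 correlates only 0.5 with true gain at the demonstration, s² in the numerator becomes 0.5s². The range is then 0.05-0.19.

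**5. Does it change the test against zero?** In the same model the mean gain before selection is 0.40 - z × T, where z is the standard normal cut-off for p. Its standardised size is lowest at p = 0.30, s = 0.30, e = 0.10: z = 0.524, mean = 0.40 - 0.524 × 0.3317 = 0.226, and 0.226/0.3317 = 0.68. With n = 60 and one-sided alpha 0.05, power at 0.68 exceeds 0.99. A test of acuity gain against zero would be expected to succeed without the gate.

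**The case against.** **Selection is disclosed, and the gate resembles real use.** Section 3.1 gives the shares and describes a rigorous screen, and Step 3.09 likens the decision to a purchase. For someone deciding after a demonstration, the gain in demonstration responders is the relevant figure. This stands as far as it goes: the extended-arm estimate is legitimate for that group. But the disclosure serves the sample size and recruitment plan, and nothing in Section 10 attaches it to the result. Section 1 speaks of a wider population.

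**The readings may be kept.** Step 3.08 may mean only that they are not a baseline, and the CRF is not in the documents. Section 10 also lists minimum reporting. A reader might infer that the readings are discarded; the documents do not show that. They show only that keeping and analysing them is not required.

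**Non-advancers are not a blank.** Diagnosis, unaided acuity and contrast, and a reason are all recorded, and the reason could separate subjects who missed four lines from those who declined. This is right, and the reason belongs in the summary. It does not supply the size of the response.

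**Demonstration acuity is not functional benefit.** Footnote 11 defines that as "ability to perform various Activities of Daily Living (ADL) with better efficacy and speed than using habitual assistive technology devices". This stands: selection acts directly on acuity, and on questionnaires and daily-living tests only through correlation.

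**The size is assumed.** This stands. If the minimum is not applied strictly, because judgement admits some subjects below four lines, the excess would be smaller than the strict-gate range.

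**Conclusion.** The point holds, and a change is worth making. Followed as written, the plan reports an acuity gain in a group chosen partly for that gain, without saying so where the result is reported. It also requires no device response from those who stop at Step 3.09.

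Only the direction of the effect is well supported. It follows from selecting on gain unless demonstration and month-3 gains are unrelated. The range of about 0.08-0.35 logMAR (roughly 1 to 3.5 lines) rests on the assumptions listed in the working and should not be quoted as a property of this trial.

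A reader might infer that the sample size is wrong, or that a positive finding would be an artefact of the gate. The documents do not support either: 60 reproduces from the stated inputs, and the test against zero does not depend on the gate. What changes is the size of the gain and whom it describes.

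**What to change.** 1. **Step 3.08.** Record on-device ETDRS acuity and contrast in the CRF for every subject demonstrated. Name the unaided comparator, because Step 3.06 allows Snellen while the gate is in ETDRS lines. Acuity and contrast are enough: in the listed order, the unaided reading and face tests come after the decision. If the CRF already has these fields, only items 2 and 3 remain.
2. **Section 10.** Summarise with-device against without-device acuity and contrast in all subjects demonstrated, for advancers and non-advancers, by diagnosis, baseline acuity, contrast and age. Tabulate the recorded reasons for not proceeding. Note that demonstration acuity is only part of functional benefit as footnote 11 defines it.
3. **Section 10 and its limitations text.** State that extended-arm results apply to subjects who passed the demonstration.

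The cost is a few CRF fields, a short analysis and two sentences, with no new test or visit. The downside for the sponsor is that the gain in all subjects demonstrated is expected to be lower than the extended-arm gain.
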